Serious Adverse Events: Expedited review will occur for all events meeting the FDA definition of SAEs – i.e., any fatal event, immediately life-threatening event, permanently or substantially disabling event, event requiring or prolonging inpatient hospitalization, or any congenital anomaly. This also includes any event that a

study investigator judges to impose a significant hazard, contraindication, side effect, or precaution. Reporting to the IRB will be done within 24 hours of the SAE.

Study Stopping Rules: If at any time during the course of the study, the PI or CO-Is judge that risk to participants outweighs the potential benefits, the PI/CO-Is shall have the discretion and responsibility to recommend that the study be terminated.

AE Reporting Guidelines

Concomitant Medications and Adverse Events: Concomitant medications (dosage, start and stop dates) will be reviewed and recorded at each visit. The study doctor will document and side effect or adverse event during Phase II.

In case of serious adverse cognitive side effects (delirium or confusion of clinical concern, with or without other symptoms like hallucinations, paranoia) or other serious side effects (e.g., cardiac, neurologic), patients will be discontinued from the study and immediately treated with the appropriate pharmacologic management (e.g., haloperidol, as needed, for delirium and psychotic symptoms).

X: References

1. Zarate CA, Jr., Singh JB, Carlson PJ, Brutsche NE, Ameli R, Luckenbaugh DA, Charney DS, Manji HK. A randomized trial of an N-methyl-D-aspartate antagonist in treatment-resistant major depression. *Archives of general psychiatry*. 2006;63:856-864.

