Retention: All patients are eligible to receive a free consultation at the DCRP immediately following the completion of all study materials. This care is supplemental to their ongoing care with their treating psychiatrist/doctor. The treating psychiatrist will be informed before any medications changes are considered.

Renumeration: All participants who complete all parts of the study will be paid \$200, and parking will be validated for the study visits. For patients that come in for the screening visit only, they will be renumerated \$20; parking will also be validated. The payment schedule for the other three visits is \$60 each.

Note, the probabilistic reward task is a monetary reward task. Patients will be told that their payment for this task, based on the money they win, will be included in their total payment for study participation.

Procedures for Informed Consent

[figure not shown]
Written informed consent will be obtained by a licensed physician from all patients before protocol-specific procedures begin. The investigator obtaining consent will explain in detail the protocol of the study, its purpose, and potential benefits to the society. Participants will be informed that they can choose to terminate the study at any time, for any reason.

Treatment Assignment and Randomization (If Applicable)

N/A; All participants will be assigned to open-label ketamine.

V. Study Procedures

Research Design Summary: The proposed research (Aims 1-3) will begin with a screening visit (Visit 1) and a medication stabilization period of ≥ 28 days (Phase I). In Phase II, 58 depressed patients meeting research criteria (specified above) will undergo baseline biomarker and psychometric assessments (Visit 2). One-to-two days later, they will receive an open-label infusion of subanesthetic intravenous ketamine (0.5mg/kg over 40 minutes), and will be monitored for 4 hours in the MGH Clinical Research Center (Visit 3). Visit 4, which will occur on the day after the ketamine infusion, will consist of the same biomarker and psychometric assessments from Visit 2 (see “Schema” for overall study outline):

Visits and Parameters to be Measured/Data to be Collected and When the Data is Collected

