MANAGEMENT: During concomitant use of these drugs, patients should be monitored for potentially excessive or prolonged CNS and respiratory depression. Patients will be counseled to avoid hazardous activities requiring mental alertness and motor coordination until they know how these agents affect them, and to notify their physician if they experience excessive or prolonged CNS effects that interfere with their normal activities.

[figure not shown]
Ketamine Administration and Monitoring: A single, open-label infusion of ketamine at a subanesthetic dose of 0.5mg/kg over 40 minutes will be administered on the morning of Visit 3 at the MGH Clinical Research Center (CRC) by a BLS and ACLS-certified licensed physician, as this dose and procedure has been previously used in depression research, (1, 24, 25) including studies completed at the MGH CRC (e.g., Protocol 2012P001042). Prior to the infusion, all patients will be fasting since midnight, except for required morning medications. Monitoring of oximetry, pulse rate, and blood pressure will be done before, during, and after the infusion. Although subanesthetic ketamine has been shown to have a favorable safety profile when given to depressed patients in research studies, (1, 24-27) there is a potential risk of adverse psychotomimetic, dissociative, and/or sympathomimetic events. Patients will be discontinued from the study if they experience serious adverse events during or after the infusion. See below for details on monitoring and rescue medications.

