Psychometric Assessments: Self- and clinician-rated assessments will take place during the study. We will administer the following scales to all participants at all visits (Visits 1-4): the Hamilton Depression Rating Scale (HDRS) (the primary dependent outcome measure) is a 28-item validated clinician-administered scale that is widely used as an observational rating measure of depression presence and severity;(34) the Montgomery Asberg Depression Rating Scale (MADRS), a 15-item validated clinical-administered scale widely used for the assessment of depression (35); Hamilton Psychiatric Rating Scale for Anxiety (HAM-A) is a 14-item validated clinician-administered scale that is widely used as an observational rating measure of anxiety presence and severity;(36) Clinically Useful Depression Outcome Scale (for the DSM-5 Anxious Distress Specifier) (CUDOS-A) is a 22-item self-rated scale for the assessment of DSM-5 anxious distress;(37) Young Mania Rating Scale (YMRS) is an 11-item clinician-rated scale for the measurements of hypomanic/manic symptoms;(38) MGH Sexual Functioning Questionnaire (SFQ) is a 7-item self-rated scale for the assessment of sexual functioning; *Snaith-Hamilton Pleasure Scale* (SHAPS) is a 14-item self-report questionnaire for the assessment of anhedonia (please loss to previously pleasurable activities);(39)

We will administer the following to all participants at Visit 1 only (screening): *Mini-International Neuropsychiatric interview (M.I.N.I.)* to assess for the presence of depression;(40) the MGH Antidepressant Treatment History Questionnaire (ATRQ), a clinician-rated scale used to determine treatment resistance in depression;(41) the *Early Trauma Inventory Self Report-Short Form* (ETISR-SF), a 29-item self-report item on early trauma history,(42) the EHI (a self-reported measure of dominant handedness), and a demographics form.

We will administer the following scales to all participants during Visit 3 (ketamine administration) only: *Brief Psychiatric Rating Scale (BPRS)* is an 18-item clinician-administered scale for the assessment of psychotic symptom constructs;(43) *Clinician Administered Dissociative States Scale (CADSS)* is a 28-item clinician-administered scale for the assessment of dissociative symptoms.(44) BPRS and CADSS will be administered at baseline, +40 minutes, +80 minutes, and +120 minutes in reference to the start of the ketamine infusion.

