Ketamine Administration and Monitoring: Ketamine is a glutamatergic receptor antagonist that has been administered to millions of patients worldwide as a general anesthetic, though its antidepressant mechanism of action (at sub-anesthetic doses) remains largely unknown. Although low-dose ketamine has been shown to have a favorable safety profile when given to depressed patients in several studies,(1, 24-27) there is a potential risk of adverse psychotomimetic, dissociative, and/or sympathomimetic events. Similar to previous studies showing efficacy and safety of intravenous ketamine in adults with mood disorders,(1, 45, 46) including studies completed at the MGH CRC (e.g., Protocol 2012P001042), ketamine will be administered at 0.5mg/kg over 40 minutes by a BLS and ACLS-certified, licensed physician at the MGH General Clinical Research Center. Patients will be monitored at the General Clinical Research Center by a medical doctor and trained nurse for changes in vital signs (i.e., heart rate, blood pressure, respiration, temperature, pulse ox, and sedation level) and for treatment-emergent side effects (i.e., as measured by the CADSS and BPRS) during administration and post-administration. Rescue medications, including intravenous labetalol, lorazepam, ondansetron, and haloperidol will be available in the event that unwanted side effects occur; participants requiring such interventions will be withdrawn from the study. PO ibuprofen and acetaminophen will also be available. The following parameters are specified in the order set for the CRC:

1. Oxygen 4 to 6 liters/min via face mask or nasal cannula PRN, SpO₂ <93% at bedside
2. Labetolol 2.5 mg IV push over 2 mins PRN BP ≥3 readings in a row of BP ≥ 160/100; may repeat every 2 to 5 mins X5. Given by MD/NP. Infusions will be stopped if BP ≥160/00 persists for more than 20 minutes. PRN for tachycardia >100 bpm; symptomatic tachycardia >100 bpm requires EKG.
3. Lorazepam 2mg IV push PRN severe agitation, attempting to pull out IV; May repeat every 2-5 minutes X 3. Given by MD/NP
4. Haloperidol 1-2mg IV push PRN delirium (not oriented to space and time, hallucinations, attempting to pull IV); May repeat every 10 minutes X 5. Given by MD/NP
5. Glycopyrrolate 0.1mg IV push PRN excessive salivary secretion; May repeat every 2-5 minutes X 3. Given by MD/NP
6. Ondansetron 4mg IV PRN severe nausea, may repeat x1 after 30 min if no effect.

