Testing of Hypotheses: Statistics and Data Analysis

Specific Aim #1: Objective and subjective measures of anxiety will be positively correlated with each other. A primary analysis will examine Pearson correlations between subjective measures of anxiety (i.e., the HDRS Anxiety-Somatization Factor Scale, HAM-A, and CUDOS-A) and eye-blink startle response. Similarly, we will examine correlations between subjective anxiety and reward responsiveness. We will analyze the data to ensure that linearity exists. If linearity does not exist, we will conduct comprehensive sub-analyses to find the best way to characterize the relationship of all data. For example, we will use covariates (e.g., clinical descriptors such as treatment failures) to determine their role in creating non-linearity.

Specific Aim #2: Greater psychophysiological and cognitive objective measures of anxiety will predict better antidepressant response to ketamine, regardless of subjective depression symptoms. We will use a nonlongitudinal linear regression model to assess the extent to which the combination of pre-treatment psychophysiological (e.g., anxiety-potentiated eye-blink startle) and cognitive reward processing (high versus low reward responsiveness) predict the antidepressant treatment response to ketamine (Visits 3 and 4). Antidepressant response to ketamine will be defined as a $\geq 50\%$ improvement in HDRS scores (primary dependent outcome measure).

Specific Aim #3: In ketamine responders, psychophysiological measurements will show a significantly larger decreases in magnitude compared to ketamine nonresponders; greater improvements will be seen in cognitive reward processing measures in ketamine responders. We will use longitudinal analyses (linear mixed effects random regression models) to analyze the effect of ketamine on

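### Patients who need a named IV rescue drug are withdrawn from the study with no provision for the Visit 4 HDRS, so Aim #2 is estimated only in patients who did not need rescue

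*Combined protocol and SAP*

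**What the plan says.** The rule is in Section V, in the Ketamine Administration and Monitoring paragraph that follows Drug to be Used. It first lists the drugs: "Rescue medications, including intravenous labetalol, lorazepam, ondansetron, and haloperidol will be available in the event that unwanted side effects occur". The consequence for a patient who needs one is given in the second half of that sentence: "participants requiring such interventions will be withdrawn from the study". The next sentence adds "PO ibuprofen and acetaminophen will also be available". The order set below it also lists oxygen and glycopyrrolate. A separate rule, under Safety and Monitoring, reads "Patients will be discontinued from the study if they experience serious adverse events during or after the infusion".

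On timing, the biomarkers are measured at Visit 2, the single infusion is at Visit 3, and "Visit 4, which will occur on the day after the ketamine infusion, will consist of the same biomarker and psychometric assessments from Visit 2". The HDRS is among the scales given at Visits 1 to 4. For Visit 3, Section V fixes clock times for the BPRS and CADSS but none for the HDRS.

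On analysis, Section VI (Specific Aim #2) begins "We will use a nonlongitudinal linear regression model to assess the extent to which the combination of pre-treatment psychophysiological" and continues with the cognitive measures, the aim being to "predict the antidepressant treatment response to ketamine (Visits 3 and 4"). Response is a fall of at least 50% in HDRS. No analysis set or missing-data method is given for this aim. Sample Size Determination sets 58 patients and recruits 70 to allow for drop-out; Sections IV and V speak of 58 enrolled and treated.

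**The concern.** Because there is only one infusion, withdrawing a patient after rescue mainly ends assessment. For Aim #2 the predictors already exist at that point. What is missing is one clinician rating at a visit already scheduled for the next day.

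The patients lost need not be a random sample. The order set ties labetalol to blood pressure and heart rate, and lorazepam to severe agitation. Section I treats heart-rate reactivity to threat as a candidate marker of anxiety, so a link between rescue and the Aim #2 predictors is plausible. If rescue also relates to antidepressant outcome, the biomarker-response association among the remaining patients differs from that among all infused patients. The 12 extra recruits replace numbers, not the kind of patient who was lost. Without Visit 4 scores, the selection cannot be examined afterwards.

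**Working it through.** **1. The plan's own figure.** Inputs from Sample Size Determination: n=58, r=0.35, two-sided α=0.05, power above 0.8. With the noncentral t test of a correlation, δ = √n·r/√(1−r²) = √58 × 0.35/√0.8775 = 2.85 on 56 df, which gives power 0.799; 80% is reached at n=59. The stated 58 therefore reproduces to within one patient. The source effect d=0.76 converts to r = 0.76/√(0.76²+4) = 0.355, consistent with the planned 0.35.

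**2. Loss of patients.** The rescue rate is not given; 10% and 20% are assumptions. Power by Fisher z with the usual small-sample term is Φ[(atanh r + r/(2(n−1)))·√(n−3) − 1.960], with atanh 0.35 = 0.3654. For n=58: (0.3654 + 0.0031) × 7.416 − 1.960 = 0.773, so power is 0.780.

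| Infused | Rescue rate | Evaluable | Power, Fisher z | Power, noncentral t |
|---|---|---|---|---|
| 58 | 0 | 58 | 0.78 | 0.80 |
| 58 | 10% | 52 | 0.73 | 0.75 |
| 58 | 20% | 46 | 0.68 | 0.70 |
| 70 | 10% | 63 | 0.81 | 0.83 |
| 70 | 20% | 56 | 0.77 | 0.78 |

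These powers hold r at 0.35 and count no other losses.

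**3. Selection when the true correlation is 0.** Let X be the biomarker and Y the HDRS improvement, both standard normal and independent. Rescue liability is L = aX + bY + √(1−a²−b²)·E, with E independent standard normal noise. Remove the upper 10% or 20% of L and correlate X with Y in the rest (simulation of millions of draws). The loadings a and b are assumptions.

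| Rescue tracks | a, b | r at 10% / 20% rescue |
|---|---|---|
| higher startle, poorer response | 0.3, −0.3 | 0.03 / 0.04 |
| higher startle, poorer response | 0.5, −0.5 | 0.08 / 0.12 |
| higher startle, better response | 0.5, 0.5 | −0.08 / −0.12 |
| startle alone | 0.5, 0 | about 0 / about 0 |

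**4. Selection when the true correlation is 0.35.** Here rescue follows a logistic model with assumed odds ratios per SD, at 5/10/20% rescue. With 2 on the biomarker only, r is 0.347/0.344/0.340 and the regression slope stays at 0.35. With 2 on both biomarker and improvement, r is 0.327/0.310/0.285. With 2 on the biomarker and 0.5 on improvement, r is 0.362/0.371/0.385. Odds ratios of 3 widen the range to 0.235-0.419.

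**5. Scale.** The approximate standard error of r, 1/√(n−3), is 0.143 at n=52 and 0.152 at n=46, so every simulated shift in step 3 is below one standard error. Steps 3 and 4 use continuous improvement; the plan also dichotomises at 50%, so the figures are indicative.

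**The case against.** The strongest reply is that rescue can contaminate the outcome itself. A reader might infer that rescue drugs matter only for Visit 4 startle in Aim #3 and that the lost HDRS scores would all be cleanly usable. The documents do not support that. Section V (Special Case of Sertraline and the Urine Drug Screen) says benzodiazepines may make ketamine less effective, and lorazepam is one of the four named drugs. Some rescued patients may also have had the infusion stopped. This stands for those patients. It is a reason to analyse them separately, not a reason to leave all rescued patients unrated, and the documents make no such statement about labetalol or ondansetron.

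Second, prediction of response among patients who received ketamine without another acute drug is a legitimate question, and Section IX describes a physiological study of biomarkers, not a clinical trial. That stands as a choice of primary population, but the choice is not stated, and the current rule rules out the other analysis.

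Third, rescue may be rare. Lorazepam and haloperidol have severe triggers, labetalol for blood pressure needs repeated readings, and screening excludes raised blood pressure. Section I also reports no difference in dissociative or psychotomimetic effects between anxious and nonanxious patients. That comparison had 15 and 11 patients and does not cover sympathomimetic effects. The rate remains unknown either way.

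Fourth, an outcome may survive. The HDRS is listed for Visit 3, Aim #2 cites Visits 3 and 4, and Section VII has rating scales completed before discharge. With no stated timing relative to the infusion, a post-infusion Visit 3 HDRS is possible but cannot be relied on.

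**Conclusion.** The point holds as a gap in the plan that is cheap to close. The rule withdraws patients from the study, not only from the infusion, and no section keeps their Visit 4 HDRS. Its loss is inferred from these two facts; it is not stated outright. On that reading, Aim #2 describes patients who did not need rescue.

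Three stronger readings are not supported:

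- **That Aim #2 is biased, or biased towards its hypothesis.** Under the assumptions above the distortion runs from about -0.12 to 0.12 when the true correlation is 0, and is about 0 when rescue depends on startle alone. The documents give neither a rescue rate nor any relation of rescue to outcome.
- **That any item in the order set triggers withdrawal.** The rule names four IV drugs. Its wording is open-ended, and whether oxygen, glycopyrrolate or the oral analgesics count must be reconciled.
- **That the sample necessarily falls short of plan.** Power is 0.73-0.68 if 58 are infused but 0.81-0.77 if 70 are. The two numbers must be reconciled.

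**What to change.** Separate withdrawal from study treatment from withdrawal from assessment. Consenting, medically able patients would keep the scheduled Visit 4 HDRS, with the rescue drug and any incomplete infusion recorded. Then:

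- Report Aim #2 with and without rescued patients, and prespecify which analysis is primary.
- Treat lorazepam-rescued and incomplete-infusion patients separately, given the protocol's own statement on benzodiazepines.
- Flag or exclude rescued patients' Visit 4 startle in Aim #3.
- State which items count as rescue for the withdrawal rule, when the Visit 3 HDRS is taken relative to the infusion, and whether 58 or 70 are to be infused.

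No change is proposed to when rescue is given or the infusion is stopped.

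The cost is a short amendment, one extra analysis and some patients with incomplete testing. Visit 4 is already scheduled.

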In light of ketamine's relatively good safety profile, all participants will be medically screened (including EKG and vital signs) prior to entering the active treatment portion of the study, to ensure healthy baseline general and cardiac functioning. In addition, as ketamine is an anesthetic that may result in respiratory depression, participants will be excluded from the study if they require sedatives or opiates. During the

administration, a medical doctor will remain in the room with a research nurse, the research assistant, and the patient, and vital signs will be monitored every 5 minutes during the 40 minutes of administration. Any concerning changes will be managed by the physicians. Criteria for discontinuation include ≥ 3 readings in a row of systolic BP ≥ 180 mmHg or diastolic BP ≥ 110 mmHg, HR ≥ 110 bpm, or symptomatic elevations in blood pressure (i.e., new onset headache, chest pain, or shortness of breath). Furthermore, the physician may choose to stop the infusion at any time if he/she believes it is in the best interest of the participant, based upon his/her clinical judgment.

Participants will stay at the General Clinical Research Center (GCRC) for up to 4 hours following the start of the administration, and will be monitored for psychotomimetic, dissociative, and sympathomimetic side effects during this time. Afterwards, they will be discharged home in the care of a responsible adult family member or caretaker after completing rating scales with the study physicians. If participants experience adverse events at home, they will be referred for evaluation at the nearest emergency department. These instructions will also be provided to the responsible adult escort prior to discharge. The participant's individual insurance plan will be responsible for covering this visit.

Prior to informed consent, potential participants will be informed of alternatives to research, and will be provided with the option to seek further psychopharmacological or psychotherapy-based interventions.

Electric Shocks

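### Sections V and VII give uncoordinated blood-pressure and heart-rate limits for the ketamine infusion, and their vital-sign times during the infusion differ

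*Combined protocol and SAP*

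**What the plan says.** **Section V, Ketamine Administration and Monitoring (the subsection containing the CRC order set).** The list is introduced with "The following parameters are specified in the order set for the CRC". Item 2 contains three rules:

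- Treatment for blood pressure: "Labetolol 2.5 mg IV push over 2 mins PRN BP ≥3 readings in a row of BP ≥ 160/100".
- Treatment for heart rate: "PRN for tachycardia >100 bpm; symptomatic tachycardia >100 bpm requires EKG".
- Stopping: "Infusions will be stopped if BP ≥160/00 persists for more than 20 minutes".

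Just before the list, the text names the intravenous rescue drugs, labetalol among them, and says "participants requiring such interventions will be withdrawn from the study".

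**Section VII, Drug Side Effects and Toxicities.** "Criteria for discontinuation include ≥ 3 readings in a row of systolic BP ≥ 180 mmHg or diastolic BP ≥ 110 mmHg". The sentence goes on to heart rate of 110 bpm or more and to symptomatic rises in blood pressure. The next sentence begins "Furthermore, the physician may choose to stop the infusion at any time". The same paragraph keeps a doctor in the room and has vital signs monitored at 5-minute intervals through the 40-minute infusion.

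**Vital-sign times elsewhere.** Section V, Study Phase II, says vital signs are to be *measured* at +0, +5, +10, +15, +20, +30 and +40 minutes during the infusion, then at +60, +90, +120 and +180. Section VI, Specific Data Variables to be Collected, repeats these times as *recorded* and adds a baseline.

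**The concern.** These are decision thresholds for a drug that the protocol itself describes as having sympathomimetic effects, and they sit in two places that do not refer to each other. Someone working from the Section VII list alone would not find the 20-minute stop that Section V makes mandatory. Someone working from the order-set items reproduced in Section V would not find the Section VII limits.

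Section VII does not say whether *discontinuation* refers to the infusion or to study participation. Nor does it say whether the three-reading condition extends to heart rate. The printed diastolic figure in the Section V stop cannot be applied as it stands.

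The reading schedule matters because several limits count consecutive readings. If the readings are spaced differently, the same patient reaches the same limit at a different time.

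There is also a possible link to the data. Intravenous rescue leads to withdrawal, and Aims 2 and 3 rely on Visit 4 measurements.

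**Working it through.** The plan states no figure to reproduce here. The check sets the limits side by side and then counts readings.

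**1. Limits compared**

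| | Section V, order-set item 2 | Section VII |
|---|---|---|
| Blood pressure, treat | 160/100 or more, three consecutive readings | not given |
| Blood pressure, stop or discontinue | 160/00 as printed, for more than 20 minutes | systolic 180 or more, or diastolic 110 or more, three consecutive readings |
| Heart rate | above 100 bpm: treatment as needed; EKG if symptomatic | 110 bpm or more: discontinuation |
| Symptomatic rise in blood pressure | not given | discontinuation |
| Study withdrawal | if intravenous rescue is required | not stated |

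**2. A case where the two lists give different answers.** Take a sustained 170/105 without symptoms and with heart rate below 110. Assume that the printed figure means 160/100, and count duration from the first high reading.

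- Section V: 170 ≥ 160 and 105 ≥ 100, so the stop applies once more than 20 minutes have passed. If first read at +5, the first reading later than +25 is +30 on either schedule.
- Section VII: 170 < 180 and 105 < 110, so no listed blood-pressure limit is met. Only the physician's discretion remains.

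**3. Cases where the two lists overlap**

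- Sustained 182/105 first read at +5: the labetalol condition and the Section VII systolic limit are both met at the third reading, +15. The Section V stop is met at +30. This does not depend on whether the printed 00 means 100, because 182/105 exceeds 160/100 as well.
- Heart rate 101 to 109 bpm (above 100, below 110, in whole beats): labetalol is permitted as needed, but no Section VII heart-rate limit is met.

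**4. Reading counts over 0 to 40 minutes**

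- Every 5 minutes: 40/5 + 1 = 9 readings.
- Listed times: 0, 5, 10, 15, 20, 30, 40 = 7 readings. The two absent are +25 and +35.

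**5. Effect on the limits.** Values are assumed sustained, and rules are assessed only at scheduled readings.

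| First high reading | Third consecutive reading: 5-minute / listed | First reading more than 20 minutes later: 5-minute / listed |
|---|---|---|
| 0 | +10 / +10 | +25 / +30 |
| +5 | +15 / +15 | +30 / +30 |
| +10 | +20 / +20 | +35 / +40 |
| +15 | +25 / +30 | +40 / +40 |
| +20 | +30 / +40 | none by +40 / none by +40 |
| +30 | +40 / +60 (after the infusion) | none by +40 / none by +40 |

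The third reading is the same on both schedules for first high readings up to +10. It comes 5 minutes later on the listed times for +15 and 10 minutes later for +20. For +30 it falls after the infusion has ended.

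**The case against.** The strongest reply is that the limits are graded: treat at a lower level, stop if that level is sustained, discontinue at a higher level. On that reading neither section requires what the other forbids. The Section VII list is also open-ended, and a physician in the room may stop the infusion at any time. This stands. A reader might infer that the two sections contradict each other outright, and the documents do not support that. The 182/105 and heart-rate 101 to 109 cases show overlap and a gap between levels. Section V does link intravenous rescue to withdrawal. What remains is that no section says the limits are tiers, and the 170/105 case shows that Section VII alone does not lead to the Section V stop.

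The placement of the Section VII criteria, between monitoring during administration and the physician's freedom to stop the infusion, suggests that the infusion is meant. The earlier Ketamine Administration and Monitoring subsection of Section V and the AE Reporting Guidelines in Section IX refer explicitly to the study when that is intended, which supports this. It is the likely reading, but it is left to inference.

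A reader might also treat 160/00 as a proven error in the plan. It is not proven: the same item prints 160/100 just before, and a digit may have been lost in typing or in text extraction. It needs confirming, no more.

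On the schedule, every listed time falls on the 5-minute grid, and Section VI calls the times recorded. If they are recording points only, the difference in step 5 disappears. Only the word *measured* in Section V, Study Phase II, points the other way. The step 5 timings also assume untreated, unchanging values assessed only at scheduled times. Labetalol may be repeated at intervals shorter than the listed gaps, and with a doctor present, readings between those times are plausible.

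Finally, the full order set is not in the documents, so whether it already carries the Section VII limits is unknown.

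**Conclusion.** The point holds as a lack of coordination between safety sections. There are two sets of blood-pressure and heart-rate limits with no stated relation, one printed figure to confirm, and two descriptions of vital-sign timing that may or may not mean the same thing. It is a minor-to-moderate correction.

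The 170/105 case rests on reading the printed figure as 160/100. The timing differences (5 to 10 minutes for a first high reading at +15 or +20, and beyond the infusion for +30) rest on the listed times being the only measurements. They are not estimates of patient risk.

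A reader might infer that withdrawal after rescue biases the Visit 4 analyses. The documents give no frequency of rescue or of stopped infusions, so that effect can be neither shown nor sized. Sample size, power and the significance level are not affected.

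**What to change.** The responsible physicians should reconcile Section V (Study Phase II, and the order-set parameters under Ketamine Administration and Monitoring), Section VI (Specific Data Variables to be Collected) and Section VII (Drug Side Effects and Toxicities) into one consistent set of treat, stop and withdraw rules. The reconciled text should:

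- say whether the limits are tiers and how treating, stopping and withdrawing relate;
- confirm the diastolic figure in the 20-minute stop;
- say whether *discontinuation* in Section VII means the infusion or the study;
- say whether the three-reading condition covers heart rate;
- give one vital-sign schedule during the infusion, and say whether the listed times are recording points only;
- appear unchanged in the CRC order set.

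No limit or schedule is proposed here. The cost is clarifying wording in the protocol and the order set, with no change to design, sample size or analysis.
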